#### 11.2 Clinical Laboratory Evaluations

Clinical laboratory evaluations include the continuous variables for hematology, and serum chemistry. The laboratory values will be presented in standard units. Summary tables and graphical presentations will only include the laboratory values that are deemed to be "on-treatment" to oral study drug as follows: All clinical laboratory values with an onset date on or after the date of first dose of oral study medication until the date of the last oral study medication plus 28 days. The laboratory values collected outside of the on-treatment period for oral study drug will only be presented in the data listings.

For visit-based summaries; the laboratory evaluations that are during the actual scheduled cycle visit (ie, EDC visit structure) will be used, otherwise, any unscheduled laboratory evaluations that are closest to and within the same actual scheduled cycle will be used. The data sets should highlight the value for the patient that was included in the summary table, wherever feasible. The summary tables and graphs will only display data if the number of observations is greater than 10 in each treatment arm.

The summary of laboratory data will include descriptive statistics of the maximum, minimum, and last value during the on-treatment period. Summaries using descriptive statistics of the change from baseline to the maximum, minimum, and last value during the on-treatment period will also be given.

Shift summary tables from baseline to the maximum on-treatment toxicity grade (CTCAE v5.0 or later) for each lab parameter will be summarized.

Figures of the mean values over time with standard error bars will be presented for key safety laboratory parameters.

This study uses a central laboratory assessment of all safety laboratory data. Local laboratory values that are clinically relevant or support eligibility will be added to the CRFs. All aggregate analyses of data will primarily be done using only the central laboratory data. The local laboratory data will be presented in patient level data listings. However, an additional maximum on-treatment toxicity grade shift from baseline grade may be presented using both local and central laboratory data.

Additional detail regarding clinical laboratory evaluations are provided in Appendix 2.Urinalysis results will be reported in patient level listings.

## 11.3 Vital Signs

The vital signs values will be presented in standard units. Summary tables and graphical presentations will only include the vital signs values that are deemed to be "on-treatment" to oral study drug as follows: all vital signs values with an onset date on or after the date of first dose of oral study medication until the date of the last oral study medication plus 28 days. The vital signs values collected outside of the on-treatment period for oral study drug will only be presented in the data listings.

For visit-based summaries; vital signs evaluated during the actual scheduled cycle visit will be used, otherwise, any unscheduled vital signs evaluations that are closest and within the same actual scheduled cycle will be used. The data sets should highlight the value for the patient that went into the summary table, wherever feasible. The summary tables and graphs will only display data if the number of observations is greater than 10 in each treatment arm.

The summary of vital sign data will include descriptive statistics of the maximum, minimum, and last value during the on-treatment period. Summaries using descriptive statistics of the change from baseline to the maximum, minimum, and last value during the on-treatment period will also be given.

#### 11.4 ECG

Local reads of ECG were collected at Screening and End of Study. Summaries using descriptive statistics of the observed value and change from baseline to end of study will also be given.

The QT interval was corrected by using both Fridericia's (QTcF) and Bazett's (QTcB) formula. Each patient's maximum QTc intervals will be classified according to the CTCAE V5 grades to the following categories: < 450 msec (Normal),  $\geq$  450 to  $\leq$  480 msec (Grade 1),  $\geq$  480 to  $\leq$  500 msec (Grade 2), and  $\geq$  500 msec (Grade 3). In addition, each patient's maximum change from baseline for QTc intervals will be classified into  $\leq$  30 msec,  $\geq$  30 to  $\leq$  60 msec, and  $\geq$  60 msec (Grade 3). The number and percentage of patients in each classified category will be presented.

## 11.5 Examination of Safety in Subgroups

The following key safety output will be further explored within subgroups based on key intrinsic factors. The key identified safety output are:

- All TEAEs;
- Grade 3 or greater TEAEs;
- Serious TEAEs;
- TEAEs with an outcome of death;
- TEAEs leading to discontinuation of oral study drug;

- TEAEs leading to dose reduction of oral study drug;
- TEAEs resulting in interruption of oral study drug;
- TEAEs resulting in dose reduction or interruption of oral study drug; and
- Shift summary tables from baseline to the maximum on-treatment toxicity grade for each clinical laboratory parameter.

The following subgroups based on key intrinsic factors will be summarized:

- Age groups ( $< 65, 65-74, \ge 75; \ge 65$ ; and < 75 years old);
- Race (White, Other, and Unknown); and
- The stratification factor used for randomization of HRD classification (tBRCA, non-tBRCA LOHhigh, non-tBRCA LOHlow, and non-tBRCA LOHunknown) and the HRD Population.

# 12 DOCUMENT REVISION HISTORY

Version	Date signed	Description
1.0	02Dec2021	Original Version
2.0	10Feb2022	Clarified the test to be chi-square for secondary endpoint of ORR instead of stratified CMH test. Clarified that the log-rank test will be used for the multiplicity testing instead of the Cox proportional hazards model. Administrative changes not affecting the statistical methods.

#### 14 APPENDICES

# Appendix 1 FACT-O (Version 4)

Below is a list of statements that other people with your illness have said are important. Please circle or mark one number per line to indicate your response as it applies to the past 7 days.

**Physical Well-being (PWB)** 

	siem wen being (1 w b)	Not at all	A little bit	Some- what	Quite a bit	Very much
1	I have a lack of energy	0	1	2	3	4
2	I have nausea	0	1	2	3	4
3	Because of my physical condition, I have trouble meeting the needs of my family	0	1	2	3	4
4	I have pain	0	1	2	3	4
5	I am bothered by side effects of treatment	0	1	2	3	4
6	I feel ill	0	1	2	3	4
7	I am forced to spend time in bed	0	1	2	3	4

Social/Family Well-being (SWB)

	and anny wen being (SWD)	Not at all	A little bit	Some- what	Quite a bit	Very much
1	I feel close to my friends	0	1	2	3	4
2	I get emotional support from my family	0	1	2	3	4
3	I get support from my friends	0	1	2	3	4
4	My family has accepted my illness	0	1	2	3	4
5	I am satisfied with family communication about my illness		1	2	3	4
6	I feel close to my partner (or the person why is my main support)	0	1	2	3	4
Q	Regardless of your current level of sexual activity, please answer the following question. If you prefer not to answer it,					

Clovis Oncology 10 February 2022

	please mark this box $\square$ and go to the next section.					
7	I am satisfied with my sex life	0	1	2	3	4

Please circle or mark one number per line to indicate your response as it applies to the past 7 days.

**Emotional Well-being (EWB)** 

	wind went being (E W B)	Not at all	A little bit	Some- what	Quite a bit	Very much
1	I feel sad	0	1	2	3	4
2	I am satisfied with how I am coping with my illness	0	1	2	3	4
3	I am loosing hope in the fight against my illness	0	1	2	3	4
4	I feel nervous	0	1	2	3	4
5	I worry about dying	0	1	2	3	4
6	I worry my condition will get worse	0	1	2	3	4

**Functional Well-being (FWB)** 

	netional (ven being (1 (vb)	Not at all	A little bit	Some- what	Quite a bit	Very much
1	I am able to work (include work from home)	0	1	2	3	4
2	My work (include work from home) is fulfilling	0	1	2	3	4
3	I am able to enjoy life	0	1	2	3	4
4	I have accepted my illness	0	1	2	3	4
5	I am sleeping well	0	1	2	3	4
6	I enjoy the things I usually do for fun	0	1	2	3	4
7	I am content with the quality of life right now	0	1	2	3	4

# Please circle or mark one number per line to indicate your response as it applies to the past 7 days.

**Additional Concerns (OCS)** 

	itional Concerns (OCS)	Not at all	A little bit	Some- what	Quite a bit	Very much
1	I have swelling in my stomach area	0	1	2	3	4
2	I am losing weight	0	1	2	3	4
3	I have control of my bowls	0	1	2	3	4
4	I have been vomiting	0	1	2	3	4
5	I am bothered by hair loss	0	1	2	3	4
6	I have a good appetite	0	1	2	3	4
7	I like the appearance of my body	0	1	2	3	4
8	I am able to get around by myself	0	1	2	3	4
9	I am able to feel like a woman	0	1	2	3	4
10	I have cramps in my stomach area	0	1	2	3	4
11	I am interested in sex	0	1	2	3	4
12	I am concerned about my ability to have children.	0	1	2	3	4

The scoring manual for FACT-O is located here: https://www.facit.org/scoring.

The 5 sub scores of the instrument (PWB, SWB, EWB, FWB, and OCS subscale scores) will only be calculated if > 50% of questions that go into the subscale are answered. FACT-O Total Score will only be calculated if > 80% of questions are answered AND none of the component subscale scores (PWB, SWB, EWB, FWB, OCS) are missing. Trial Outcome Index (TOI) will only be calculated if > 80% of questions are answered AND none of the component subscale scores (PWV, FWB, OCS) are missing.

## **Appendix 2** Clinical Laboratory Evaluations

#### CTCAE Version

The summary of laboratory data includes tables based on NCI-Common Terminology Criteria for Adverse Events (CTCAE), which is a descriptive terminology utilized for Adverse Event (AE) reporting. A grading (severity) scale is provided for each AE term. In general, CTCAE version 5.0 is used; however, in some cases version 4.03 is substituted as quantitative grading is not available in version 5.0.

The table below lists terms using version 4.03 or a slight modification to version 5.0.

CTCAE Term	Notes
Hyperglycemia Hypophosphatemia Hyponatremia	Version 5.0 is based on clinical observations or interventions initiated that are not available in the clinical database. Version 4.03 is applied.
Hyperkalemia Hypernatremia	Version 5.0 is based on a combination of laboratory results and interventions. The logic associated with laboratory results is used.
Hypokalemia	Both grades 1 and 2 use <lln-3.0 1="" 2="" 2.<="" additionally="" applied="" are="" available="" clinical="" database.="" grade="" in="" interventions="" is="" l.="" mmol="" not="" observations="" or="" range="" requires="" td="" that="" the="" to="" used.=""></lln-3.0>

#### **Grading of Central and Local Laboratory Data**

The central laboratory provides CTCAE grades according to their lab Tox Grade Report. However, in some instances the Report indicates grading is derived without the use of a baseline result where v5.0 requires use of upper limit of normal (ULN) for normal baseline and increments above baseline for abnormal baseline. Therefore, the CTCAE grading criteria will be applied in a consistent manner across all laboratory assessment using stacked data that includes both central and local results.

#### Normal Reference Ranges

A reference range is a set of values that includes upper and lower limits based on a group of otherwise healthy people. The values may depend on age, gender, and specimen type, and can also be influenced by circumstantial situations such as fasting and exercise.

Normal reference ranges for central laboratory assessments are contained within the data provided by the central laboratory. Each of the local laboratories provided normal ranges specific to the laboratory in which the test was done. These local ranges were entered into EDC and applied to results via the lab admin tool.

#### **Liver Function Tests**

Baseline results for four Liver Function Tests (LFTs); Alanine aminotransferase (ALT), Aspartate aminotransferase (AST), Alkaline phosphatase (ALP), and bilirubin will not receive a numeric grade (grade 1-5). They will be categorized in relation to the ULN (eg,  $\leq$  ULN, > ULN-3  $\times$  ULN, > 3  $\times$  ULN-5  $\times$  ULN). Shifts in grade from baseline to maximum on-treatment post-baseline for these events (ALT increased, ALP increased, AST increased, and blood bilirubin increased) will not be summarized.

#### **Creatinine Clearance**

Estimated GFR (eGFR) by Cockcroft-Gault is collected in both central and local laboratory data. These results will be provided in data listings and will not be summarized.

Renal impairment at baseline (creatinine clearance) will be re-calculated using serum creatinine, age and weight using the Cockcroft-Gault formula.

Female 
$$CL_{cr} = (140 - age) \times Body Weight (kg) \times 0.85$$
  
 $\begin{bmatrix} 72 \times Serum Creatinine \end{bmatrix}$ 

This formula expects weight to be measured in kilograms and creatinine to be measured in mg/dL; the calculated units are mL/min.

#### **CTCAE Grading: Hematology**

CTCAE Description	Grade 1	Grade 2	Grade 3	Grade 4
Anemia	100<= AVAL <lln< td="">80<= AVAL <100	AVAL <80		</lln<>	80<= AVAL <100	AVAL <80	
Lymphocyte count decreased	0.8<= AVAL <lln< td="">0.5<= AVAL < 0.8	0.2<= AVAL < 0.5	<0.2	</lln<>	0.5<= AVAL < 0.8	0.2<= AVAL < 0.5	<0.2
Lymphocyte count increased		4< AVAL <=20	AVAL >20	
Neutrophil count decreased	1.5<= AVAL <lln< td="">1<= AVAL <1.5	0.5<= AVAL <1	AVAL <0.5	</lln<>	1<= AVAL <1.5	0.5<= AVAL <1	AVAL <0.5
Platelet count decreased	75<= AVAL <lln< td="">50<= AVAL <75	25<= AVAL <50	AVAL <25	</lln<>	50<= AVAL <75	25<= AVAL <50	AVAL <25
White blood cell decreased	3.0<= AVAL <lln< td="">2.0<= AVAL <3.0	1.0<= AVAL<2.0	AVAL <1.0	</lln<>	2.0<= AVAL <3.0	1.0<= AVAL<2.0	AVAL <1.0

# **CTCAE Grading: Chemistry**

CTCAE						
Description	Grade 1	Grade 2	Grade 3	Grade 4		
Hypoalbuminemia	30<= AVAL <lln< td="">20<= AVAL <30	AVAL <20		</lln<>	20<= AVAL <30	AVAL <20			
	If baseline is normal:					
	ULN< AVAL	2.5xULN< AVAL	5xULN< AVAL	AVAL		
	<=2.5xULN	<=5xULN	<=20xULN	>20xULN		
		If baseline is ab	1			
Alkaline phosphatase increased	2xBASE<= AVAL <=2.5xBASE	2.5xBASE< AVAL <=5xBASE	5xBASE< AVAL <= 20xBASE	>20xBASE		
		If baseline is n	ormal:			
	ULN< AVAL <=3xULN	3xULN< AVAL <=5xULN	5xULN< AVAL <=20xULN	AVAL >20xULN		
		If baseline is ab	normal:			
Alanine						
aminotransferase increased	2xBASE<= AVAL <=2.5xBASE	2.5xBASE< AVAL <=5xBASE	5xBASE< AVAL <=20xBASE	>20xBASE		
		If baseline is n	ormal:			
	ULN< AVAL	3xULN< AVAL	5xULN< AVAL	AVAL		
	<=3xULN	<=5xULN	<=20xULN	>20xULN		
	If baseline is abnormal:					
Aspartate	1.5 D.4.GE :		5 DAGE AND			
aminotransferase increased	1.5xBASE<= AVAL <=3xBASE	3xBASE< AVAL <=5xBASE	5xBASE< AVAL <=20xBASE	>20xBASE		
Morousou	TIVIE CABILEE	If baseline is n	II.	20.131132		
	ULN< AVAL <=1.5xULN	1.5xULN< AVAL <=3xULN	3xULN< AVAL <=10xULN	AVAL >10xULN		
	If baseline is abnormal:					
Blood bilirubin increased	BASE<= AVAL <=1.5xBASE	1.5xBASE< AVAL <=3xBASE	3xBASE< AVAL <=10xBASE	>10xBASE		
mereasea	· 1.5ADIAGE	SADIAGE	1.5<= AVAL	> TOAD/ISE		
Hypocalcemia	2.0<= AVAL <lln< td="">1.75<= AVAL <2.0	<1.75	AVAL <1.5	</lln<>	1.75<= AVAL <2.0	<1.75	AVAL <1.5		
Hypercalcemia	ULN< AVAL <=2.9	2.9< AVAL <=3.1	3.1< AVAL <=3.4	AVAL >3.4		
	ULN< AVAL		10.34< AVAL			
Cholesterol high	<=7.75	7.75< AVAL <=0.34	<=12.92	AVAL >12.92		
Creatinine increased	ULN< AVAL <=1.5xULN	1.5xBASE< AVAL <=3xBASE; 1.5xULN< AVAL <=3xULN	AVAL >3xBASE; 3xULN< AVAL <=6xULN	AVAL >6xULN		
Hypoglycemia	3.0<= AVAL <lln< td="">2.2<= AVAL <3.0	1.7<= AVAL <2.2	AVAL <1.7	</lln<>	2.2<= AVAL <3.0	1.7<= AVAL <2.2	AVAL <1.7		
JF - 8-J - 3	22.122.2211		13.9< AVAL			
Hyperglycemia	ULN< AVAL <=8.9	8.9< AVAL <=13.9	<=27.8	AVAL >27.8		
Hypokalemia		3.0<= AVAL <lln< td="">2.5<= AVAL <3.0	AVAL <2.5	</lln<>	2.5<= AVAL <3.0	AVAL <2.5		

Clovis Oncology 10 February 2022

CTCAE Description	Grade 1	Grade 2	Grade 3	Grade 4
			6.0< AVAL	
Hyperkalemia	ULN< AVAL <=5.5	5.5< AVAL <=6.0	<=7.0	AVAL >7.0
Hypomagnesemia	0.5<= AVAL <lln< td="">0.4<= AVAL <0.5	0.3<= AVAL <0.4	AVAL <0.3	</lln<>	0.4<= AVAL <0.5	0.3<= AVAL <0.4	AVAL <0.3
Hypermagnesemia	ULN< AVAL <=1.23		1.23< AVAL <=3.30	AVAL >3.30
Hypophosphatemia	0.8<= AVAL <lln< td="">0.6<= AVAL <0.8	0.3<= AVAL <0.6	AVAL <0.3	</lln<>	0.6<= AVAL <0.8	0.3<= AVAL <0.6	AVAL <0.3
Hyponatremia	130<= AVAL <lln< td="">	120<= AVAL <130	AVAL <120	</lln<>		120<= AVAL <130	AVAL <120
Hypernatremia	ULN< AVAL <=150	150< AVAL <=155	155< AVAL <=160	AVAL >160
Hypertriglyceridemia	1.71<= AVAL <=3.42	3.42< AVAL <=5.7	5.7< AVAL <=11.4	AVAL >11.4

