**CTCAE Grading: Chemistry** 

CTCAE Grading: (						
CTCAE Description	Grade 1	Grade 2	Grade 3	Grade 4		
Hypoalbuminemia,						
g/L	30<= AVAL <lln< td="">20<= AVAL <30	AVAL <20		</lln<>	20<= AVAL <30	AVAL <20			
		If baseline is n				
	ULN< AVAL	2.5xULN< AVAL	5xULN< AVAL	AVAL		
	<=2.5xULN	<=5xULN	<=20xULN	>20xULN		
		If baseline is ab		T		
Alkaline phosphatase	$2xBASE \le AVAL$	2.5xBASE< AVAL	5xBASE< AVAL			
increased, U/L	<=2.5xBASE	<=5xBASE	<= 20xBASE	>20xBASE		
		If baseline is n	ormal:	1		
	ULN< AVAL	3xULN< AVAL	5xULN< AVAL	AVAL		
	<=3xULN	<=5xULN	<=20xULN	>20xULN		
		If baseline is ab	normal:			
Alanine						
aminotransferase	$2xBASE \le AVAL$	2.5xBASE< AVAL	5xBASE< AVAL			
increased, U/L	<=2.5xBASE	<=5xBASE	<=20xBASE	>20xBASE		
		If baseline is n	ormal:	1		
	ULN< AVAL	3xULN< AVAL	5xULN< AVAL	AVAL		
	<=3xULN	<=5xULN	<=20xULN	>20xULN		
	JAOLIV	If baseline is ab		ZUKULIV		
Aspartate		Ti cuscime is as	Horman.			
aminotransferase	1.5xBASE<= AVAL	3xBASE< AVAL	5xBASE< AVAL			
increased, U/L	<=3xBASE	<=5xBASE	<=20xBASE	>20xBASE		
		If baseline is n	ormal:			
	ULN< AVAL	1.5xULN< AVAL	3xULN< AVAL	AVAL		
	<=1.5xULN	<=3xULN	<=10xULN	>10xULN		
	If baseline is abnormal:					
Blood bilirubin	BASE<= AVAL	1.5xBASE< AVAL	3xBASE< AVAL			
increased, umol/L	<=1.5xBASE	<=3xBASE	<=10xBASE	>10xBASE		
Hypocalcemia,	1101121122	, and the second	10.121152	10.151102		
mmol/L	2.0<= AVAL <lln< td="">1.75<= AVAL <2.0	1.5<= AVAL <1.75	AVAL <1.5	</lln<>	1.75<= AVAL <2.0	1.5<= AVAL <1.75	AVAL <1.5		
Hypercalcemia,						
mmol/L	ULN< AVAL <=2.9	2.9< AVAL <=3.1	3.1< AVAL <=3.4	AVAL >3.4		
Cholesterol high,			10.34< AVAL			
mmol/L	ULN< AVAL <=7.75	7.75< AVAL <=0.34	<=12.92	AVAL >12.92		
		1.5xBASE< AVAL				
		<=3xBASE;	AVAL >3xBASE;			
Creatinine increased,	ULN< AVAL	1.5xULN< AVAL	3xULN< AVAL			
umol/L	<=1.5xULN	<=3xULN	<=6xULN	AVAL >6xULN		
Hypoglycemia,	-					
mmol/L	3.0<= AVAL <lln< td=""><math>2.2 \le AVAL \le 3.0</math>	1.7<= AVAL <2.2	AVAL <1.7	</lln<>	$2.2 \le AVAL \le 3.0$	1.7<= AVAL <2.2	AVAL <1.7		
Hyperglycemia,			13.9< AVAL			
mmol/L	ULN< AVAL <=8.9	8.9< AVAL <=13.9	<=27.8	AVAL >27.8		
Hypokalemia,						
mmol/La		3.0<= AVAL <lln< td="">2.5<= AVAL <3.0	AVAL <2.5	</lln<>	2.5<= AVAL <3.0	AVAL <2.5		
Hyperkalemia,						
mmol/L	ULN< AVAL <=5.5	5.5< AVAL <=6.0	6.0< AVAL <=7.0	AVAL >7.0		
Hypomagnesemia,						

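### In both SAPs the ALT grading row for abnormal baseline duplicates the alkaline phosphatase row, an undeclared inconsistency that should be checked against CTCAE v5.0

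*SAP*

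**What the plan says.** Both SAPs state that laboratory grades follow CTCAE v5.0, with ULN multiples when baseline is normal and baseline multiples when it is abnormal (Grading of Central and Local Laboratory Data, in each appendix). Each appendix also lists the terms for which v4.03 or a modified v5.0 rule is used. These are glucose, phosphate, sodium and potassium terms; ALT is not among them.

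In the MONO SAP chemistry table:

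- ALT, normal baseline: Grade 1 is "ULN< AVAL <=3xULN" and Grade 2 is "3xULN< AVAL <=5xULN". AST has the same limits.
- ALT, abnormal baseline: Grade 1 is "2xBASE<= AVAL <=2.5xBASE" and Grade 2 is "2.5xBASE< AVAL <=5xBASE". ALP has the same limits.
- AST, abnormal baseline: Grade 1 is "1.5xBASE<= AVAL <=3xBASE" and Grade 2 is "3xBASE< AVAL <=5xBASE".

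The COMBO SAP table shows the same pattern. Its ALT Grade 2 starts at "2.5xBASE< AVAL", as for ALP, while its AST Grade 1 starts at "1.5xBASE<= AVAL".

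**The concern.** ALT follows AST in one half of the table and ALP in the other, and neither SAP explains why. The ALT block comes directly after the ALP block, so a copied row is the natural explanation.

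What is at stake is the count of low-grade ALT abnormalities. Section 11 of the COMBO SAP summarises on-study laboratory parameters, including liver function, by worst CTCAE grade. The protocol's safety overview (Section 1.1.1.2.3) puts ALT/AST elevation among the most common findings with rucaparib and describes the most common adverse events as mainly Grade 1 to 2. Those are the grades that this row affects. The table would be applied as written, so the grades would change without anything in the output to show it.

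**Working it through.** No sample size, power or alpha figure is involved. The check compares the rows and then grades each ratio of on-treatment to baseline value under two sets of limits.

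**Step 1. Compare the upper limits of Grades 1/2/3 for each liver test** (chemistry tables, same values in both SAPs).

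| Test | Normal baseline (× ULN) | Abnormal baseline (× baseline) | Same multipliers? |
|---|---|---|---|
| ALP | 2.5 / 5 / 20 | 2.5 / 5 / 20 | yes |
| ALT | 3 / 5 / 20 | 2.5 / 5 / 20 | **no** |
| AST | 3 / 5 / 20 | 3 / 5 / 20 | yes |
| Bilirubin | 1.5 / 3 / 10 | 1.5 / 3 / 10 | yes |

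For abnormal baseline, Grade 1 starts at 2 × baseline for ALP, 2 × for ALT, 1.5 × for AST and 1 × for bilirubin. ALT is therefore the only one of the four whose two rows disagree, and its abnormal-baseline row equals the ALP row at every limit.

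**Step 2. Grade the ratio r = on-treatment ALT / baseline ALT** under the ALT row as written and under the AST multipliers. Ratios from 1.00 to 21.99 were graded in steps of 0.01.

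| r | ALT row as written | AST multipliers |
|---|---|---|
| below 1.5 | none | none |
| **1.5 to <2** | **none** | **Grade 1** |
| 2 to 2.5 | Grade 1 | Grade 1 |
| **>2.5 to 3** | **Grade 2** | **Grade 1** |
| >3 to 5 | Grade 2 | Grade 2 |
| >5 to 20 | Grade 3 | Grade 3 |
| >20 | Grade 4 | Grade 4 |

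Two bands change, in opposite directions. A ratio of exactly 2.5 is Grade 1 under both.

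**Step 3. Express the bands in ULN.** Inclusion criterion 10 (Protocol 4.2) caps ALT at 1.5 × ULN at entry, so an abnormal baseline should usually lie between 1 and 1.5 × ULN. At the cap, the ungraded band is 1.5 × 1.5 = 2.25 to 1.5 × 2 = 3.0 × ULN. The Grade 2 band is above 1.5 × 2.5 = 3.75, up to 1.5 × 3 = 4.5 × ULN.

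Example: an eligible patient with baseline 1.4 × ULN rises to 2.7 × ULN. The ratio is 2.7 / 1.4 = 1.93, so no grade is given as written; the AST multipliers would give Grade 1. A patient with normal baseline who reaches the same 2.7 × ULN is Grade 1.

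**Step 4. Trace where the grades are used.** COMBO SAP Section 11 reports liver function by worst grade. COMBO 11.3 and MONO 11.2 call for grade shifts for every laboratory parameter, and MONO 11.5 repeats them by subgroup. The Liver Function Tests paragraph in both appendices, however, excludes ALT, AST, ALP and bilirubin from shift summaries. If that specific rule governs, the COMBO worst-grade summary is the clear remaining use.

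**The case against.** The strongest reply is that the CTCAE v5.0 text is not reproduced in the documents. Nothing in them requires ALT and AST to share abnormal-baseline limits, or baseline multiples to mirror ULN multiples. A reader might infer that ALT rises are definitely mis-graded; the documents alone do not prove that. They show an exact duplicate of another test's row, a break with ALT's own normal-baseline row, and no declared departure. That supports a probable copying slip and a request to verify it. Damage in reading the PDF is an unlikely explanation, because two separate SAPs carry the same row. Both tables also carry the same impossible Grade 2 cholesterol range (above 7.75 and at most 0.34), so slips do recur across the two appendices.

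The reply on impact largely stands:

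- No planned analysis compares ALT with AST. The comparisons are between arms, and every arm is graded by the same row, so the row does not in itself favour an arm. It can still blur low-grade counts.
- The exclusion of liver tests from shift tables removes what would otherwise be the main output.
- Adverse events of ALT or AST increase are graded and recorded on the eCRF under the protocol (7.5.4.1). Nothing says they are derived from this table.
- The protocol's listing of clinically significant laboratory abnormalities covers Grades 3 and 4 only (9.7.2), and these do not change.
- A reader might also infer that dosing decisions are affected. The ALT/AST hold limits for IV drug (Protocol 5.6.1.2) are ULN multiples regardless of baseline. The oral-drug ALT/AST rules (5.6.1.1.1) turn on Grade 3 or 4 and on recovery to Grade 2, a boundary that is the same under both sets of limits.

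**Conclusion.** The inconsistency is real and present in both SAPs, and the internal evidence for a copied row is strong. Its consequence is minor. Relative to the AST multipliers, ALT is graded one step too low at 1.5 to <2 × baseline and one step too high at >2.5 to 3 × baseline. Only the no-grade, Grade 1 and Grade 2 categories of ALT laboratory summaries are touched, and only in patients with abnormal baseline ALT. The share of such patients is not given, so the number of changed grades cannot be estimated. Efficacy is not involved.

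The conclusion assumes that ALT is meant to follow AST for abnormal baseline, as it does for normal baseline. Only the CTCAE text can settle that. It also assumes that the exclusion in the Liver Function Tests paragraph overrides the general instruction to tabulate shifts for each parameter. If it does not, the shift tables are affected as well.

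**What to change.** Check the ALT abnormal-baseline row against the cited CTCAE v5.0.

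- If ALT follows AST, as the internal pattern indicates, change Grade 1 to 1.5–3 × baseline and Grade 2 to >3–5 × baseline. That is two cells in each of two appendices, four in all.
- If the present limits are intended, add ALT to the list of departures from v5.0 in both appendices.

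After a correction, re-derive the COMBO ALT grades and the worst-grade summary. For MONO, the sponsor team was unblinded to Arms B and D on 23 March 2022 (COMBO SAP 3.5). A correction there should be recorded as made after unblinding, with its reason, and any ALT grade output that uses the row re-derived.

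The cost is a table correction and a re-run of ALT grading for COMBO, plus a documented change and a check of existing outputs for MONO. No new data are needed.

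### Bilirubin Grade 1 for an abnormal baseline starts at no change, so a raised bilirubin that stays the same is graded as toxicity

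*SAP*

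**What the plan says.** The MONO SAP (Appendix 2) and the COMBO SAP (Appendix B) carry the same chemistry grading bounds. For ALP, ALT, AST and bilirubin, grades are multiples of ULN if baseline is normal and multiples of baseline if it is abnormal. The Grade 1 bounds are:

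- Bilirubin, abnormal baseline: "BASE<= AVAL <=1.5xBASE". In the COMBO table the same bounds are split over two lines.
- Bilirubin, normal baseline: "ULN< AVAL <=1.5xULN".
- ALT, abnormal baseline (ALP is the same): "2xBASE<= AVAL <=2.5xBASE".
- AST, abnormal baseline: "1.5xBASE<= AVAL <=3xBASE".

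The part of each appendix on grading central and local results describes the version 5.0 rule as use of the "upper limit of normal (ULN) for normal baseline and increments above baseline for abnormal baseline".

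On baseline values of the four liver tests, both appendices say "They will be categorized in relation to the ULN"; the lowest example category is at or below ULN. Both then drop the baseline-to-maximum grade shifts for these tests. Section 11 of the COMBO SAP nevertheless plans to summarise liver function by worst grade.

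**The concern.** A grade for an increased value should need an increase. As written, the bilirubin row needs none, so a stable patient enters the toxicity count. Such patients can be enrolled: Protocol Section 4.2 admits bilirubin up to 1.5 x ULN, and up to 2 x ULN with Gilbert's syndrome.

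There is a related gap in the trigger for the baseline-multiple rows. The tables say only that baseline is abnormal, without saying on which side, while the same appendices define a reference range as having both an upper and a lower limit. A programmer therefore has to choose a meaning.

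At stake is the accuracy of the Grade 1 bilirubin counts. No efficacy result is involved.

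**Working it through.** The plan gives no figure to reproduce here, so the check applies the rows literally.

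**Step 1: bilirubin, abnormal baseline.** Let r = AVAL / BASE. As written:

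- Grade 1: 1 <= r <= 1.5
- Grade 2: 1.5 < r <= 3
- Grade 3: 3 < r <= 10
- Grade 4: r > 10

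No change is r = 1, which is Grade 1 whatever the reference range. For illustration, assume ULN = 21 umol/L (the documents give no ranges):

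| Baseline | AVAL | r | Grade as written | Grade with BASE < AVAL |
|---|---|---|---|---|
| 22 (just above ULN) | 22 | 1.0 | 1 | none |
| 31.5 (1.5 x 21) | 31.5 | 1.0 | 1 | none |
| 42 (2 x 21) | 42 | 1.0 | 1 | none |
| 22 | 19.8 | 0.9 | none | none |
| 22 | 33 | 1.5 | 1 | 1 |

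Only r = 1 changes. Grades 2 to 4 are the same under both forms.

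**Step 2: comparison with the neighbouring rows.** With a normal baseline, the bilirubin lower bound is strict, so AVAL exactly at ULN is not graded. With an abnormal baseline, AST starts at r = 1.5 and ALT and ALP start at r = 2, so an unchanged enzyme value is not graded. Bilirubin is the only one of the four tests in which no change earns a grade.

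**Step 3: the undefined trigger.** Two readings of abnormal were applied: outside the range on either side, and above ULN only. Assumed ranges are bilirubin 3-21 umol/L and ALT 6-34 U/L.

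| Test and baseline | AVAL (in range) | r | Either side | Above ULN only |
|---|---|---|---|---|
| Bilirubin 2 | 4 | 2.0 | Grade 2 | none |
| Bilirubin 2 | 7 | 3.5 | Grade 3 | none |
| Bilirubin 2 | 21 | 10.5 | Grade 4 | none |
| ALT 5 | 10 | 2.0 | Grade 1 | none |
| ALT 5 | 13 | 2.6 | Grade 2 | none |
| ALT 5 | 26 | 5.2 | Grade 3 | none |

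Defining the trigger as above ULN removes every in-range grade but leaves the unchanged raised bilirubin at Grade 1. The strict bound removes that. The two edits deal with separate problems.

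**The case against.** The best defence is that the consequence is slight. In a worst-grade summary, the equality alters a patient's grade only if baseline is abnormal and the highest on-treatment value exactly equals it; any rise up to 1.5 x baseline is Grade 1 under either form. Both appendices drop grade shifts for the four liver tests. Adverse event tables use MedDRA-coded events, not this table. Potential drug-induced liver injury (Protocol Section 8.9) and the IV-drug hepatic hold and discontinuation rules (Sections 5.6.1.2 and 5.6.4.2) use multiples of ULN. All of this stands and sets the size of the point. It does not make the row correct. The shift exception is also not repeated where the SAPs call for shifts in each laboratory parameter (MONO Sections 11.2 and 11.5, COMBO Section 11.3).

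A reader might infer three stronger things, none of which the documents support:

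- *That the SAPs grade normal-range values as toxicity.* This needs abnormal to include values below the lower limit. Neither SAP says so. Every row concerned is for an increased value, the paired normal-baseline rows start at ULN, and baseline liver tests are categorised against ULN only. The context favours the high side; the fault is that this is left unstated.
- *That the error favours one arm.* The protocol reports common ALT and AST rises on rucaparib, but an unchanged enzyme value is not graded, so the equality does not arise for those tests. Protocol Section 1.2 says the rises generally come without substantial bilirubin elevation, which gives no ground for expecting an arm difference in the bilirubin row.
- *That a patient count can be given.* Assuming, say, that 1-10% of 500 MONO patients have a low baseline would give 5 to 50 (0.01 x 500 and 0.10 x 500). That prevalence is not in the documents, and the count would still depend on the reading rejected above.

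**Conclusion.** The point holds for bilirubin. Both SAPs grade an unchanged raised bilirubin as Grade 1, against their own description of the rule and against the normal-baseline row. This is true whichever meaning of abnormal is used. The effect is confined to Grade 1 bilirubin counts, mainly in the COMBO worst-grade liver summaries, and its size cannot be computed because the documents give neither reference ranges nor baseline distributions. The examples above rest on assumed ranges; the conclusion for r = 1 does not.

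The undefined trigger is a matter of clarification, not a demonstrated error. It would do harm only if programmed to include baselines below the lower limit.

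**What to change.** In COMBO SAP Appendix B, change Grade 1 bilirubin for an abnormal baseline to BASE < AVAL <= 1.5xBASE. In the same edit, state that for ALP, ALT, AST and bilirubin an abnormal baseline means baseline > ULN and a normal one means baseline <= ULN, in line with the appendix's own baseline categories.

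Make the same correction in MONO SAP Appendix 2. The COMBO SAP (Section 3.5) records that the MONO primary analysis was performed on 23 March 2022, so for MONO this should be a documented correction that applies to any further output. Check whether any bilirubin grades were tabulated, and rerun only those.

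The cost is one inequality and one definition in each appendix, the matching programming condition, and a rerun of any affected bilirubin grade table. No new data are needed.
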